### 3.5.2 Laboratory variables

Blood and urine samples for determination of clinical chemistry, hematology, and urinalysis parameters will be taken at the times detailed in the CSP and will be assessed in a central laboratory. The parameters outlined in Section 5.2.1, Table 4 of the CSP will be collected.

In summaries, figures, and listings, lab results and normal ranges will be presented in System International (SI) units. Eosinophil data will be presented in both SI and conventional units (cells/ $\mu$ L) in summaries.

For the purposes of clinical chemistry, hematology, and urinalysis shift tables, baseline will be defined as the last available non-missing assessment prior to first dose of randomized treatment, and maximum or minimum value post-baseline will be calculated over the entire post-baseline period, including the post-treatment period.

Changes in hematology and clinical chemistry variables between baseline and each post-baseline assessment will be calculated. The change from baseline is defined as the post-baseline visit value minus the baseline visit value. There will be no imputation for missing values. For values recorded with a leading greater than or less than ('>', '<') symbol, the reported numeric value will be used for analysis and the value with the symbol will be included in the listings, unless otherwise specified. For example, a value of <0.01 will be analyzed as 0.01 and listed as <0.01.

Absolute values will be compared to the relevant reference range and classified as low (below range), normal (within range or on limits), or high (above range). The central reference ranges will be used for laboratory variables. All values (absolute and change) falling outside the reference ranges will be flagged.

Urinalysis data will be categorized as negative (0), positive (+), or strongly positive (++, +++, or >+++)) at each timepoint.

For the liver function tests: aspartate aminotransferase (AST), alanine aminotransferase (ALT), alkaline phosphatase (ALP), gamma-GT (GGT), and total bilirubin (TBL), the multiple of the central laboratory upper limit of the normal (ULN) range will be calculated for each data point.

$$\text{Multiple} = \text{Value} / \text{ULN}$$

That is, if the ALT value was 72 IU/L (ULN=36) then the multiple would be 2.

Patients who meet any of the following criteria at any point during the study will be flagged:

- AST  $\geq 3x$  ULN
- ALT  $\geq 3x$  ULN
- TBL  $\geq 2x$ ULN

### 3.5.3 Local electrocardiogram

Electrocardiogram (ECG) measurements will be performed at Visit 1 and the FU visit. The outcome of the overall evaluation is to be recorded as normal/abnormal in the electronic case report form (eCRF) by the Investigator/authorized delegate, with any abnormalities being recorded as not clinically significant or clinically significant.

### 3.5.4 Physical examination

Complete and brief physical examinations will be performed at timepoint specified in Tables 2 and 3 of the CSP.

Baseline data will be collected at Visit 1. Any new finding(s) or aggravated existing finding(s), judged as clinically significant by the Investigator, will be reported as an AE as described in Section 6.3 of the CSP.

### 3.5.5 Vital signs

Pre-dose vital signs (pulse, systolic blood pressure, diastolic blood pressure, respiration rate, and body temperature) will be obtained in accordance with the visit schedule provided in the CSP.

Changes in vital signs variables between baseline and each subsequent scheduled assessment will be calculated. Baseline is defined as the last value prior to the first dose of randomized treatment. The change from baseline is defined as the post-baseline visit value minus the baseline visit value. There will be no imputation for missing values.

Absolute values will be compared with the reference ranges in [Table 2](#) and classified as low (below range), normal (within range or on limits), or high (above range). All values (absolute and change) falling outside the reference ranges will be flagged.

**Table 2** Vital signs reference ranges

Parameter	Standard units	Lower limit	Upper limit
Diastolic Blood Pressure (DBP)	mmHg	60	120
Systolic Blood Pressure (SBP)	mmHg	100	160
Pulse Rate	Beats/min	40	120
Respiratory Rate	Breaths/min	8	28
Body Temperature	Celsius	36.5	38
Weight	kg	40	200

Body mass index (BMI) will be calculated from the height and weight as follows:

$$\text{BMI (kg/m}^2\text{)} = \text{weight (kg)} / (\text{height [m]})^2$$

### **3.6 Pharmacokinetic variables**

Pharmacokinetic trough concentration will be assayed for each visit where serum samples are collected.

In addition, estimation of PK parameters, ie,  $C_{max}$ ,  $t_{max}$ , and  $AUC_{[0,28d]}$  will be computed for the first dosing cycle using a noncompartmental estimation method.  $C_{max}$  and  $T_{max}$  are direct measurements of the maximum observed concentration and the time to reach the  $C_{max}$ , respectively, during the first dosing cycle.

### **3.7 Immunogenicity variables**

Anti-drug antibodies assessments will be conducted utilizing a tiered approach (screen, confirm, titer). The presence of nAb will be tested in all ADA-positive samples using a ligand binding assay.

For each patient, the following response variables will be evaluated. Samples taken post dose on the day of IP administrations are excluded from analysis.

- ADA positive at any visit (including baseline and unscheduled visits)
- ADA positive at both post-baseline and baseline
- ADA positive at post-baseline only
- ADA positive at baseline only
- nAb positive at any visit

Safety outcomes by ADA status (if the number of occurrences ADA responses is sufficient) will also be evaluated.

## **4. ANALYSIS METHODS**

### **4.1 General principles**

The analysis of the primary and secondary efficacy endpoints will include all data captured during the 12-week double-blind treatment period, defined as the period after administration of randomized IP at Visit 4 (Week 0) and the conclusion of Visit 10 (Week 12), inclusive. This includes data regardless of whether study treatment was prematurely discontinued or delayed, and/or irrespective of protocol adherence, unless the patient withdraws consent to study participation. The statistical analyses will compare benralizumab with placebo. The analysis of safety endpoints will include all data captured during the on-study period, defined as the period after first administration of randomized IP at Visit 4 (Week 0) and the conclusion of the scheduled post-treatment FU visit (Week 11), inclusive.

The data analyses will be conducted using the SAS® System 9.2 (SAS Institute Inc., Cary, NC) or higher version. Pharmacokinetic analyses will be performed using WinNonlin (version 6.3, or higher, Certara, L.P., St. Louis, MO).

Summary data will be presented in tabular format by treatment group. Descriptive statistics on continuous variables will be summarized by treatment group using mean, standard deviation, median, quartile, and range as applicable, while categorical data will be summarized using frequency counts and percentages. When data are summarized by time, the values recorded against the scheduled timepoints listed in the protocol will be used. When assessing minimum/maximum increases or decreases during the study, all assessments, including unscheduled assessments will be used. For analysis assessing change from baseline, only patients with both baseline and at least 1 evaluable post-baseline measure will be included.

Given there is a single primary endpoint and treatment comparison, no formal testing strategy will be used for the analysis in this study.

All hypothesis testing will be reported using 2-sided tests. All p-values apart from the primary analyses of the primary endpoint will be nominal. All p-values will be rounded to 4 decimal places.

The absolute change from baseline is computed as (*visit value* – *baseline value*). Percent change from baseline is computed as  $([visit\ value - baseline\ value]/baseline\ value) \times 100\%$ . If either a visit value or the baseline visit value is missing, the absolute change from baseline value and the percent change from baseline will also be set to missing.

The prior medications, categorized according to the WHO Drug Reference List dictionary which employs the Anatomical Therapeutic Chemical (ATC) classification system, will be summarized by treatment group as frequency and percentage of patients reporting usage.

The concomitant medication will be categorized according to the WHO Drug Reference List dictionary which employs the Anatomical Therapeutic Chemical (ATC) classification system. The frequency and percentage of patients taking concomitant medications and non-drug therapies during the treatment period will be summarized by drug class and drug name using the ATC codes.

## **4.2 Analysis methods**

### **4.2.1 Patient disposition**

Patient disposition will be summarized using the all patients analysis set. The total number of patients will be summarized for the following groups: those who enrolled, and those who were not randomized (and reason). The number and percentage of patients within each treatment group will be presented by the following categories: randomized, received treatment with study drug, did not receive treatment with study drug (and reason), completed treatment with study drug, discontinued treatment with study drug (and reason), discontinued treatment with

study drug but completed study follow-up, completed study, and withdrawn from study (and reason).

Screen failure information will be listed for the all patients analysis set.

The number of patients randomized by country and center will also be summarized by treatment group in the FAS.

#### **4.2.2 Demography data and patient characteristics**

Demography data such as age, gender, race, and ethnicity will be summarized by treatment group for all patients in the FAS. Age will be derived from the date of informed consent date-of-birth, rounded down to the nearest integer. For patients in country where date of birth is not recorded, the age as recorded in the eCRF will be used.

Various baseline characteristics will also be summarized by treatment for the FAS. These include maintenance asthma medications, maintenance ICS medications, medical and surgical histories, FEV1 (pre- and post-BD) at baseline, and respiratory disease characteristics including age at onset of asthma, number of exacerbations in the previous 12 months, and number of exacerbations requiring hospitalizations in the previous 12 months.

The following will be summarized for patients in the FAS and repeated by region and for the body plethysmography sub-study set:

- Patient characteristics (weight, height, BMI, baseline eosinophil count)
- Baseline lung function data (FEV1 [L], FEV1 [% PN], FVC [L], FVC [% PN], FEV1/FVC, FEF 25-75% [L/S], reversibility (%))
- ACQ-6 score
- Respiratory disease characteristics

Medical and surgical histories will be summarized by MedDRA Preferred Term (PT) within a MedDRA System Organ Class (SOC).

The number of patients remaining on treatment, patients discontinued IP but still in study follow-up, and patients who withdraw from the study will be presented by treatment group and scheduled visit.

#### **4.2.3 Prior and concomitant medications**

The number and percentage of patients taking maintenance asthma medications, including ICS/LABA fixed dose combinations, at baseline will be summarized.

The number and percentage of patients who take prior medications, those who take allowed concomitant medications, and those who take disallowed concomitant medications during the study will be presented by treatment group. Concomitant medications will be classified

according to the WHO Drug Dictionary (WHODD). The summary tables will present data by generic term within the ATC code.

#### **4.2.4 Study Treatments**

##### **4.2.4.1 Exposure**

Exposure to IP will be calculated in days as:

$$\text{Last dose date of IP} - \text{first dose date of IP} + 1,$$

and will be summarized by treatment group for the safety analysis set.

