Investigational product, dosage and mode of administration

Benralizumab 30 mg/mL solution for injection in an accessorized pre-filled syringe (APFS) will be administered at the study center subcutaneously (SC) every 4 weeks for 3 doses (Day 0, Day 28 [± 3 days], and Day 56 [± 3 days]).

Statistical methods

Approximately 230 subjects in total and 115 subjects in each treatment group are needed for this study based on the primary objective of the study to determine the effect of benralizumab on the time course of change (onset and maintenance of effect) of pre-bronchodilator (BD) FEV₁.

Subjects will be randomized in a 1:1 ratio to benralizumab or placebo. In order to have balanced number of subjects for region and the body plethysmography sub-study the randomization will be stratified for these variables.

The primary analysis method for primary endpoint, the change from baseline in pre-BD FEV₁ will be compared between benralizumab and placebo using a repeated measures analysis. Treatment group will be fitted as the explanatory variable; region, visit and treatment*visit interaction as fixed effects and baseline pre-bronchodilator FEV₁ as a covariate. The first post-baseline timepoint where the p-value for the mean difference between benralizumab and placebo is less than or equal to 0.05 will be used to determine time to onset of effect. The average over the mean differences between benralizumab and placebo based on the change from baseline (Visit 4, Day 0) to Days 28 (Visit 8), 56 (Visit 9) and 84 (Visit 10) in pre-BD FEV₁ will be used to determine if the study is positive as well as maintenance of effect. Contrasts will be used to obtain estimates of the treatment differences over Days 28, 56 and 84 as well as at each timepoint separately.

Efficacy analysis for the main study will be performed using the full analysis set, which consists of all randomized subjects who received at least 1 dose of investigational product.

Efficacy analyses for the body plethysmography sub-study will include the subset of patients who are randomized as part of the sub-study as described for the full analysis set.

All safety variables will be summarized descriptively. The safety analysis will be performed using the safety analysis set.

	PAGE
TITLE PAGE	1
VERSION HISTORY	2
PROTOCOL SYNOPSIS.....	3
TABLE OF CONTENTS.....	8
1. INTRODUCTION	16
1.1 Background and rationale for conducting this study	16
1.2 Rationale for study design, doses and control groups.....	18

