## 1.2 Study design

This is a randomized, double-blind, parallel group, placebo-controlled study designed to evaluate the onset of effect and safety of a fixed 30 mg dose of benralizumab administered subcutaneously (SC) to patients with severe, uncontrolled asthma. Approximately 230 patients with peripheral blood eosinophil counts  $\geq 300$  cells/ $\mu$ L will be randomized globally to receive SC benralizumab 30 mg or placebo.

After enrolment, eligible patients will enter a 5-week screening/run-in period. Patients who meet eligibility criteria will enter a 12-week treatment period and receive 30 mg benralizumab or placebo at Day 0, Day 28 (+/- 3 days), and Day 56 (+/- 3 days). An End-of-Treatment (EOT) visit will be conducted at Day 84 (Week 12) and a follow-up (FU) visit will be conducted at Day 112 (Week 16).

See the clinical study protocol (CSP) Section 4, Tables 2 and 3 for a detailed list of visits and assessments.

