##### **4.2.4.2 Study treatment compliance**

Study treatment compliance will be summarized by treatment group for the FAS and calculated as:

$$\text{Study treatment compliance} = (\text{total doses administered} / \text{total doses expected}) \times 100.$$

Patients who received no study treatment will have zero compliance. Total number of doses expected includes all visits with protocol scheduled IP administration on or before a subject's IP discontinuation or treatment complete date.

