#### **4.2.10 Pharmacokinetic analyses**

The PK analyses will be performed at or under the guidance of AstraZeneca Research and Development.

Benralizumab serum concentrations and derived PK parameters will be summarized using descriptive statistics at each visit. In addition to the standard statistics, geometric mean and coefficient of variation (CV%) based on log-transformation will be presented for PK data. For the computation of geometric means, arithmetic means and medians, the BLQ data are set to LLOQ/2 before computation.

For non-compartment analysis (NCA), only patients with at least three evaluable serum PK observations post first dose (collected on day 3, day 7 and either day 14 or pre-dose on day 28) will be included.

When PK concentration data is missing on scheduled visit, data from unscheduled visits will be included based on the adjusted analysis defined visit window in Section 2.2.2; on dosing visits (ie, Baseline, Days 28 and 56), pre-dose values only are included. For subjects who prematurely discontinued study drug, PK data collected after the last dose date + 28 days (one dosing cycle) +3 days (visit window) will be excluded from PK analysis.

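### The SAP's exposure formula counts days from first to last injection and leaves out the dosing interval after the last dose, so three four-weekly doses read as 57 days and one dose as 1 day

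*SAP*

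**What the plan says.** SAP 4.2.4.1 starts its definition with "Exposure to IP will be calculated in days as" and takes "Last dose date of IP" as the end point. It subtracts the first dose date and adds 1. The result is a number of days, "and will be summarized by treatment group for the safety analysis set". No dosing interval is added after the last injection, and no other section of either document gives a different exposure definition. SAP Section 6, which lists changes from the protocol, does not mention it.

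The schedule is set out in SAP 1.2: "Patients who meet eligibility criteria will enter a 12-week treatment period and receive 30 mg benralizumab or placebo at Day 0", with further doses at Days 28 and 56, each within 3 days. The protocol synopsis describes the regimen as "every 4 weeks for 3 doses".

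Two other SAP rules bear on the point:

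- SAP 4.2.10, for patients who stop study drug early: "PK data collected after the last dose date + 28 days (one dosing cycle) +3 days (visit window) will be excluded from PK analysis". Here the SAP itself calls 28 days one dosing cycle.
- SAP 4.2.4.2 defines compliance as doses administered over doses expected. The denominator is limited as follows: "Total number of doses expected includes all visits with protocol scheduled IP administration on or before a subject's IP discontinuation or treatment complete date".

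**The concern.** Last minus first plus 1 is a natural count for a drug taken daily, where the last dose covers roughly the day on which it is taken. For an injection given every 4 weeks it credits the final dose with a single day. A reader of the study report would see about 57 days of exposure for fully treated patients beside a 12-week treatment period, and 1 day for a patient given one injection with a 28-day interval.

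The formula also uses only two dates, so it cannot show what happened between them. Protocol 3.10.1 lets a patient miss the second dose, receive the third and stay in the study. No planned table counts patients by number of doses received. What is at stake is whether the exposure summary describes treatment received in a usable way.

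**Working it through.** The documents state no expected exposure in days, so there is no figure of the plan's own to reproduce. The check is date arithmetic.

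**Inputs.** Dosing days 0, 28 and 56, the last two within 3 days (SAP 1.2). Current formula: last − first + 1 (SAP 4.2.4.1). Length of one dosing cycle: 28 days (SAP 4.2.10). Treatment period: 84 days (Protocol 8.5; 12 weeks in SAP 4.1).

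**Current formula against last − first + 28, in days:**

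| Doses received | Current | With last cycle | Shortfall |
|---|---|---|---|
| 1, 2 and 3 | 56 − 0 + 1 = 57 | 56 − 0 + 28 = 84 | 27/84 = 32% |
| 1 and 3 (second missed) | 56 − 0 + 1 = 57 | 56 − 0 + 28 = 84 | 27/84 = 32% |
| 1 and 2 | 28 − 0 + 1 = 29 | 28 − 0 + 28 = 56 | 27/56 = 48% |
| 1 only | 0 − 0 + 1 = 1 | 0 − 0 + 28 = 28 | 27/28 = 96% |

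The ±3-day window makes the full-course values 54 to 60 days under the current formula and 81 to 87 with the last cycle. For doses 1 and 2 they are 26 to 32 and 53 to 59. Keeping the +1 in the revised formula adds one day throughout: 85, 57 and 29.

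The shortfall is the same 27 days for every patient not cut short by withdrawal or death. A difference in mean days between arms is therefore hardly changed. Levels, percentages and ratios are what shift, most of all for early stoppers.

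**Compliance under SAP 4.2.4.2:**

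- Full course: 3/3 = 100%.
- Second dose missed, third given: 2/3 = 67%.
- One dose, recorded discontinuation date before the Day 28 visit: 1/1 = 100%.
- One dose, recorded discontinuation date on or after the Day 28 visit but before Day 56: 1/2 = 50%.

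Compliance therefore identifies the missed second dose, which exposure cannot. For a patient who stops after one dose, the result depends on how the discontinuation date is recorded, and the documents do not say. Protocol 3.10.1 places the discontinuation visit about 4 weeks after the last dose, so either outcome is possible. Against the three planned doses that patient would score 1/3 = 33%.

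**Where the variable is used.** SAP 4.2.5.1 (primary analysis) does not use it. SAP 4.2.9.1 defines time at risk for adverse event rates as running from first dose to the Week 16 follow-up visit, nominally Day 112.

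**The case against.** The strongest reply is that the formula is transparent, applies equally to both arms and feeds no other output. That stands. A reader might infer that adverse event rates or patient-years are understated, but SAP 4.2.9.1 has a separate denominator, and SAP 4.2.4.1 plans a summary in days with no patient-year total.

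A reader might also infer that the SAP contradicts itself. It does not. The 28-day rule in SAP 4.2.10 decides which pharmacokinetic samples to exclude after early stopping, and the 12-week period in SAP 4.1 is an analysis window. Neither defines exposure. They only show that a 28-day interval is already in the sponsor's own vocabulary.

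Nor is 84 days a true value. Protocol 3.9.1.1 equates 16 weeks with 5 half-lives, so one half-life is 112/5 = 22.4 days, and 28 days is only 28/22.4 = 1.25 half-lives. Drug is still present after that. The percentages above are distances from a dosing-interval convention, not from a measured duration.

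Finally, early stoppers are not hidden. SAP 4.2.2 shows numbers remaining on treatment by arm and visit, SAP 4.2.1 reports discontinuations with reasons, and SAP 4.2.9.1 breaks down injection site reactions by number of administrations. None of these is a table of patients by doses received, so a modest gap remains.

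**Conclusion.** The point holds as a weakness in a reporting definition. The summary labelled exposure is the span between first and last injection: nominally 57, 29 and 1 days for three doses, for doses 1 and 2, and for a single dose. With the 28-day cycle counted after the last dose these become 84, 56 and 28 days. The figures assume dosing on the nominal days and no withdrawal or death within 28 days of the last dose.

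The consequence is limited to the descriptive exposure summary in the safety set. Efficacy inference and adverse event rates are unaffected. It would be tempting to say that compliance does nothing to fill the gap. The documents do not support that, because compliance does show a missed second dose as 2/3. It can, however, show 100% after a single dose, depending on the recorded discontinuation date. The change is worth making because it is cheap, not because a conclusion of the trial depends on it.

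**What to change.** In SAP 4.2.4.1, define exposure as min(last dose date + 28 days, date of study withdrawal or death) − first dose date. State whether the count includes the +1: without it a full course is 84 days, with it 85.

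Add the number and percentage of patients who received 1, 2 and 3 doses, by arm. This table is needed whichever formula is kept, because the revised one also gives 84 days when the second dose is missed. Compliance against the three planned doses can be shown beside the existing measure.

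The dates needed are already collected. The cost is one derivation and one small table. The text should say that 28 days is a dosing-interval convention and not the full duration of drug presence. The added compliance figure will look slightly less favourable than the existing one.
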